4. **Can or will minors who are:**

- i) married, widowed, divorced; or
- ii) the parent of a child; or
- iii) a member of any of the armed forces; or
- iv) pregnant or believes herself to be pregnant; or
- v) living separate and apart from his/her parent or legal guardian, and is managing his/her own financial affairs

be approached for study participation for either themselves or their child?

Yes No

5. **Can or will wards of the state and/or children at risk of becoming wards of the state be enrolled (this includes foster children or any child that is in state custody)?**

Yes No

6. **Can or will cognitively impaired adults (adults with impaired-decision making capacity) or adults who may lose the capacity to consent be enrolled?**

Yes No

7. **Can or will prisoners be enrolled?**

Yes No

8. **Can or will students and/or employees be targeted for enrollment in this research?**

Yes No

9. **Transgender Subjects: Are you recording sex or gender for your study?**

Yes No

a. Is there a scientific and/or safety rationale for collecting information on whether a subject is transgender? Yes No

If **Yes**, respond to all of the following:

- i. **Provide the scientific/safety rationale for collecting information on whether a subject is transgender:** We do not want to exclude subjects from enrolling into the study based on sex or gender. We feel it is important to know whether the sex of the subject because that could be a confounding variable in terms of how one describes anxiety, pain, and satisfaction.
- ii. **Are transgender individuals eligible for participation in this study?** Yes No
If **No**, *Provide the scientific or safety rationale for excluding transgender or gender nonconforming individuals:*
- iii. **Check to confirm that relevant questions for transgender and gender nonconforming individuals have been incorporated into relevant study documents (i.e. protocol eligibility, screening forms, demographic questionnaires, surveys), per the [website guidance](#).**

H. Adverse Event Monitoring

H.1 Definitions

Define adverse events (AEs), serious adverse events (SAEs), and unanticipated problems for your study:
N/A

H.2 Reporting Procedures

1. *Describe the protocol-specific reporting procedures, including who will be responsible for each step (e.g., PI, Data Coordinating Center, Medical Monitor), which forms should be completed, timeframes for reporting, how reports will be distributed, and what follow-up is required:* N/A
2. *Include specific details of reporting procedures for:*
 - a. Deaths, life-threatening events, pregnancies: N/A
 - b. Other SAEs: N/A
 - c. Other AEs: N/A
 - d. Other UPS: N/A

H.3 Reportable New Information

Check to confirm that reportable new information will be reported to the IRB per the Tufts Health Sciences IRB's [Reportable New Information policy](#). If your reporting plan to the IRB differs from the IRB's policies, please describe it in detail or specify where this information is in the protocol:

I. Statistical Considerations

I.1 Study Endpoints

1. *Describe the primary and secondary study endpoints:* Primary study endpoint: Pain rating of the peripheral intravenous catheter insertion; Secondary study endpoint: Satisfaction rating of the peripheral intravenous catheter insertion
2. *Describe any primary or secondary safety endpoints:* N/A

I.2 Statistical Analysis

1. *Describe the statistical analyses that will be performed for this study:* Continuous variables will be analyzed via the Student's t-test and presented as mean +/- standard deviation. Categorical data will be analyzed via Chi-square test and presented as number and percentages. The intention-to-treat analysis will be used in this study. A P-value <0.05 will be considered statistically significant.
2. *Provide a power analysis:* Since there is currently no published study available comparing the two interventions that we plan on studying, we chose the study sample size based on the sample size rule of thumb for medical trials.¹³ The purpose of this study is to conduct a preliminary pilot trial for a potential future main trial designed with 90% power and two-sided 5% significance.

I.3 Number of Subjects

1. *Specify the number of subjects to be enrolled in total across all sites:* or N/A this is not a multicenter study.
2. *Specify the number of subjects to be enrolled at the Tufts site. Subjects who sign an ICF are considered “enrolled”. For studies that have a separate screening ICF, this number is the number of subjects who sign a screening ICF:* The goal will be to have a total of 30 subjects sign an ICF and complete the study based on the previously published sample size rule of thumb for medical trials.¹³
 - a. *Provide the rationale for enrolling this number of subjects at the Tufts site:* Although unlikely, subjects might sign ICF and then change their mind within a few minutes while the research team member is preparing to perform the peripheral intravenous catheter insertion. To ensure we have 30 subjects complete the study, we will enroll up to 40 subjects in this trial.
 - b. *Estimate the number of subjects expected to be enrolled at the Tufts site (i.e. sign the screening or study ICF) as well as the number needed to complete the study at the Tufts site:* Subjects will only be enrolled in the study for the duration of the peripheral intravenous catheter insertion procedure and the time it takes to answer the questionnaire; therefore, in theory, only one or two subjects will be enrolled at the same moment.
 - c. *If a large number of withdrawals and/or dropouts is expected, explain why:* N/A

I.4 Data Management

1. *Describe the data analysis plan, including descriptions of the data:* The only data that will be collected is what is described in the questionnaire above.
2. *Provide a power analysis:* As described above, since there is currently no published study available comparing the two interventions that we plan on studying, we chose the study sample size based on the sample size rule of thumb for medical trials.¹³ The purpose of this study is to conduct a preliminary pilot trial for a potential future main trial designed with 90% power and two-sided 5% significance.
3. *Describe the steps that will be taken to secure the data (e.g., training, authorization of access, password protection, encryption, physical controls, certificates of confidentiality, and separation of identifiers and data) during storage, use, and transmission:* Data will be collected in an envelope and stored in a locked cabinet in the PI's office. Only the research team members will have access to the data for analysis purposes. Data will not have subject identifying information on it.
4. *Describe any procedures that will be used for quality control of collected data:* Data entry will be confirmed by two research team members.
5. *Describe how data and specimens will be handled study-wide as follows:*
 - a. *What information will be included in that data or associated with the specimens:* Please see section “F.2 Procedures” for the data that will be collected. No specimens will be collected.
 - b. *Where and how data or specimens will be stored:* Data will be stored in a locked cabinet in the PI's office (as described above).
 - c. *How long the data or specimens will be stored:* Data will be stored at least until the results of the study will be published.
 - d. *Specify who will have access to the data or specimens:* The Research team will have access to the data.
 - e. *Specify who is responsible for receipt or transmission of the data or specimens:* The PI will be responsible for the receipt of the data.

- f. **Specify how data and specimens will be transported:** Data will be transported in a closed envelope from the preoperative area and to the PI's office, where it will be stored in a locked cabinet. If data will need to be transferred between research team members for statistical analysis purposes, the word [SECURE] will be included in the subject line of all emails.
- g. **Specify the plan for study data retention and storage (accounting for research team turnover):** Data will remain secure in the PI's office, in a locked cabinet.

I.5 Randomization

Will subjects be randomized?

Yes No

If Yes respond to all of the following:

1. **Describe the randomization procedures, including the ratio of subjects randomized to each study arm:** We will use <http://www.graphpad.com/quickcalcs/index.cfm> to generate a randomized sequence, with a ratio of subjects 1:1 in each arm. <https://www.ncbi.nlm.nih.gov/pmc/articles/PMC3136079/>
2. **Describe the blinding procedures:** The Co-I's that will be conducting the statistical analysis will be blinded to which study arm the subjects were assigned to. N/A the study will not be blinded.

J. Drugs or Devices

1. Will the research involve drugs?

Yes No

If Yes, respond to all of the following:

- a. **If the drug is investigational (has an IND) identify the holder of the IND:** The drug, Lidocaine 2%, is not an investigational drug. It is a commonly used drug that is widely available.
- b. **Describe your plans to store, handle, and administer study drugs so that they will be used only on subjects and be used only by authorized investigators** N/A - this drug is used throughout the hospital for many procedures.
- c. **Who on the research team, in addition to the Principal Investigator, will be accountable for drug(s):** The PI and the Co-Is have access to Lidocaine 2% when they are interacting with patients.
- d. **Who will interface with the pharmacy:** The research team members will remove Lidocaine 2% from the Pyxis machine. The pharmacy fills the Pyxis machine.
- e. **If pre-printed orders will be created to obtain study drug(s) from the pharmacy, describe the procedures for reviewing and verifying the accuracy of the pre-printed orders prior to their being implemented:** N/A, there are no pre-printed orders
- f. **If computerized order sets are created and/or infusion devices need to be programmed to administer an investigational drug, indicate the mechanism to pre-review and verify their accuracy, including who will be involved in this process from the research team, pharmacy, and nursing:** or N/A, there are no computerized orders sets and/or infusion devices.
- g. **The study drug or procedure (including beneficial health care procedures) will be available to subjects after participation in the study:** Yes N/A
- h. **There are medications or other substances that should not be taken while participating in the study. A list of these are incorporated into the ICF or submitted to the IRB as a subject handout:** Yes N/A

i. *Handouts or instructions sheets that will be given to subjects on how to administer study drug(s) have been submitted to the IRB:* Yes N/A

2. Will the research involve devices?

Yes No

If Yes, respond to all of the following:

- a. *If the device has an IDE or a claim of abbreviated IDE (non-significant risk device) identify the holder of the IDE/Abbreviated IDE:* N/A
- b. *Describe your plans to store, handle, and administer study devices so that they will be used only on subjects and be used only by authorized investigators* The device does not have to be locked up and can be used by healthcare providers outside the study. This device is widely used throughout other hospitals.
- c. *Specify who will be responsible for the costs of implantation or placement of the device in subjects' bodies?*: or N/A, the device will not be implanted or placed inside the body.
- d. *Specify who will be responsible for the costs of removing the device from subjects' bodies?*: or N/A, the device will not be removed from the body.
- e. *Specify the cost of the device and who will be responsible for the cost:* The SEMC anesthesiology department will be responsible for the cost of the device. Buzzy® XL Healthcare price is \$99.95. It is designed for multi patient disinfection. or N/A, the device will be provided free of charge.
- f. *Who on the research team, in addition to the Principal Investigator, will be accountable for device(s):* The co-investigators.
- g. *Who will interface with the sponsor:* N/A
- h. *The study device or procedure (including beneficial health care procedures) will be available to subjects after participation in the study:* Yes N/A
- i. *Handouts or instructions sheets that will be given to subjects on how to use study device(s) have been submitted to the IRB:* Yes N/A

K. Study Administration

K.1 Setting

1. *Describe the sites / locations where your research team will conduct the research:* St. Elizabeth's Medical Center
2. *The research will take place at an international site, and the International Guidance and International Checklist were utilized:* Yes N/A

K.2 Registration

1. *Describe the steps the research team will take to ensure that a subject is appropriately enrolled or registered in the study prior to receiving any study intervention (e.g. describe and submit any protocol eligibility checklist that will be used, specify who on the research team will confirm eligibility and that consent was documented, etc.):* Enrollment into the study will be very shortly after the consent process, so the Co-I who will be obtaining consent will not start performing any procedure until he/she obtains the consent.

K.3 Resources Available

1. *Describe the roles/tasks of each research team member here (or alternatively, you may submit any current Delegation of Authority Log you may have which already has this information completed):* The Co-investigators will be enrolling subjects into the study and will be the ones who will be administering the treatment and collecting data. The PI and the Co-I's will be performing the statistical analysis and reviewing each others computations to ensure accuracy.
2. *Describe the qualifications (e.g., training, experience) of the PI and research team to perform their roles. Provide enough information for the IRB to determine the PI and research team are qualified to conduct the proposed research. Alternatively, you can submit the current CVs for the research team instead:* The PI is an anesthesiology attending at St. Elizabeth's Medical Center. The Co-I's are second year anesthesiology resident physicians (aka CA-1's). They have all at least completed medical school training and one year of residency. They are all qualified to obtain consent from patients and have significant experience doing so.
3. *Describe the coverage plan to address any issues (including subject safety issues) that occur while the PI is away and/or unavailable. The research team member designated to serve as the acting PI in the PI's absence should have similar training and expertise as the PI:* N/A
4. *Describe the process to ensure the research team members have adequate oversight and are adequately trained regarding the protocol, study procedures, and their roles and responsibilities:* Prior to enrollment of subjects, the PI will review the protocol, study procedures, and roles/responsibilities with each one of the Co-I's.
5. *Medical or psychological resources that subjects might need, such as for emergencies or medical issues, are available for the study:* Yes N/A

K.4 IRB Review

1. *Check to confirm that an appropriate IRB registered with the OHRP, will review and approve this study.*
2. *Check to confirm that any amendments to the protocol or informed consent documents will be reviewed and approved by the IRB prior to use, unless required to eliminate an apparent immediate hazard to subjects.*

K.5 Multi-Site Research

Is this a multi-site study where Tufts is the sponsor, primary grant recipient, or coordinating site?:

Yes No

K.6 Community-Based Participatory Research

Can or will this study involve community-based participatory research?

Yes No

K.7 Sharing Results with Subjects

Will results (overall study results or individual subject results, such as results of investigational diagnostic tests, genetic tests, or incidental findings) be shared with subjects or others (e.g., the subject's primary care physician or the subject's treating physician)?

Yes No

L. References

Provide a list of references for all citations included in the protocol

1. Hadaway L. Short peripheral intravenous catheters and infections. *Journal of infusion nursing : the official publication of the Infusion Nurses Society*. 2012;35(4):230-240.

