1. **Describe the relevant prior experience and gaps in current knowledge:** Intravenous peripheral catheter insertion is one of the most common procedures in all health care settings,^{1,2} but it often causes pain and anxiety for patients. A myriad of techniques have been explored to reduce patient discomfort, such as topical anesthesia,³⁻⁵ cooling of the skin,⁶ vibration,⁷ and even distraction with flash lights.⁸ Some literature is available on a reusable, thermomechanical device called Buzzy® (MMJ Labs, Atlanta, GA), which combines cold with vibration and has been reported to be very effective in reducing needle-related procedural pain in children.⁹ However, so far, there is limited data available in regards to whether this device can improve the patient experience with intravenous peripheral catheter insertion for adults.^{7,10}
2. **Describe any relevant preliminary data:** Baxter et al.¹⁰ conducted a preliminary study comparing pain reported in healthy adult volunteers undergoing venous access and found that those who received Buzzy® had significantly less pain than those with no prophylactic intervention. In comparison, Redfern et al.⁷ conducted a randomized clinical trial on adult patients undergoing intravenous catheter insertion prior to elective orthopedic surgical procedures and found no significant difference in mean pain score between the Buzzy group and the control group. However, as the authors of Redfern et al.⁷ suggest, Buzzy® might not have been effective in that particular adult population possibly because of the timing when Buzzy® was applied to the patients.
3. **Provide the scientific or scholarly background for, rationale for, and significance of the research based on the existing literature and how it will add to existing knowledge:** A systematic review and meta-analysis reviewed the effectiveness of current pharmacological methods for reducing the pain associated with intravenous catheter insertion in adults and found that intradermal lidocaine 2% is the most effective

pharmacological methodology.¹¹ Although intradermal lidocaine 2% injection is effective, it is important to note that it requires the use of an additional needle stick.

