Considering the potential benefits of Buzzy® to the patients, healthcare workers, hospital, and environment, we would like to conduct a non-inferiority randomized control trial to compare the effectiveness of Buzzy® to intradermal lidocaine 2% injection for intravenous catheter insertion in adult patients. However, since there is no published data available comparing the effectiveness of intradermal lidocaine 2% injection with that of Buzzy® for peripheral intravenous catheter insertion in adult patients, we would like to begin by conducting a pilot randomized control trial to establish a baseline and then to potentially use the results of this pilot study to calculate the necessary sample size needed for the future non-inferiority trial.

4. *Describe the relevance and usefulness of the objectives:*

Undergoing surgery or any health care procedure is often anxiety provoking for patients. If intravenous peripheral catheter insertion could be made less painful, thousands of patients could benefit. Furthermore, if Buzzy® is found to be an effective methodology for relieving pain associated with peripheral intravenous catheter insertion in adult patients, then more health care providers may end up utilizing the device, resulting in a potential decrease in needle-stick injuries, smaller financial burden, and less environmental pollution.

5. *Specify whether or not this is the first time the study drug, device, or intervention/procedure will be used in humans. If there has been experience with the study drug, device, or intervention/procedure in humans, detail the experience to date: Yes No, this is not the first time the study drug, device, or intervention/procedure will be used in humans*

6. *Is there an active control group?*

Yes No

If Yes, respond to all of the following:

a. *Check to confirm that the active control is an established effective intervention. If it is not, clarify how it is ethically justified to use this control in the study:* The active control group will be the intradermal lidocaine 2% injection. The use of intradermal lidocaine 2% injection is part of the standard of care at our hospital. Furthermore, a systematic review and meta-analysis demonstrated that

intradermal lidocaine 2% is the most effective pharmacological method for reducing the pain associated with intravenous catheter injection in adults.¹¹

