Co-I's will be CA-1 (PGY2) anesthesiology physician residents at St. Elizabeth's Medical Center. They all will have approximately the same level of performing informed consent and of performing peripheral intravenous catheter insertion. The PI will be an anesthesiology attending physician who will ensure that all of the Co-I's are well versed on the study protocol, informed consent process, use of intradermal lidocaine, use of Buzzy® device, and the peripheral intravenous catheter insertion technique. The Co-I's will utilize the Operating Room Scheduling Board to learn about the scheduled patients for the day. All of these patients will require a peripheral intravenous catheter for the scheduled procedure. If the patient does not yet have a working peripheral intravenous catheter, the Co-I will approach his/her patient and as part of the anesthesia consent process will explain that the Co-I will need to place a peripheral intravenous catheter, so that the patient can receive anesthesia during the operation. While obtaining consent for anesthesia, the Co-I will identify if the patient fits the inclusion criteria for the study and does not meet any of the exclusion criteria. If the patient does satisfy the inclusion criteria, then the Co-I will explain that insertion of a peripheral intravenous catheter may cause some discomfort. The Co-I will explain that some providers at this institution choose to administer the peripheral intravenous catheter without any pain preventative techniques while some choose to inject a numbing medication under the skin prior to the placement of the peripheral intravenous catheter. Also, some providers at other institutions use the Buzzy® device, which is a combination of an ice pack and a vibrator in the shape of a bumble bee, to place a peripheral intravenous catheter on children. This device is FDA approved. There is significant literature documentation that this Buzzy® device helps children feel less pain with peripheral intravenous catheter placement; however, the Buzzy® device has not been utilized that much in adult patients. The Co-I will explain that we are conducting a study to compare the effectiveness of Buzzy® device to that of the injection of the numbing medication under the skin. The Co-I will then ask

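### F.2's verbal explanation describes the two techniques unevenly before an unblinded, self-reported primary endpoint: a plausible expectation bias whose direction and size the documents do not settle

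*Combined protocol and SAP*

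**What the plan says.** F.2 (Procedure) sets out what the co-investigator explains before asking whether the patient wants to hear more. On current practice, it says that some providers at the hospital use nothing and that "some choose to inject a numbing medication under the skin prior to the placement of the peripheral intravenous catheter". On the device, it states "This device is FDA approved" and then "There is significant literature documentation that this Buzzy® device helps children feel less pain". The same sentence adds a caveat: "the Buzzy® device has not been utilized that much in adult patients". After that come the consent form, the patient's questions, consent and the randomisation sheet. The same co-investigator then applies the technique and places the catheter.

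The background section (B.1) gives adult evidence that this explanation leaves out. Item 2 reports a preliminary study in healthy adult volunteers in which "those who received Buzzy® had significantly less pain than those with no prophylactic intervention", and a randomised trial in adults before elective orthopaedic surgery that "found no significant difference in mean pain score between the Buzzy group and the control group". Items 3 and 6a cite a systematic review and meta-analysis; item 6a summarises it as showing that "intradermal lidocaine 2% is the most effective pharmacological method for reducing the pain" of this procedure in adults.

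The primary endpoint (I.1) is the pain rating, a 0 to 10 number that the patient circles. Satisfaction, the secondary endpoint, is a 1 to 5 self-rating. I.5 describes blinding for the analysts only. F.2 has the patient put the answers in an envelope without showing them to the co-investigator.

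**The concern.** A patient cannot be blinded to a vibrating ice pack versus an injection. When the outcome is the patient's own rating, what the patient has been led to expect can move the score without any difference in analgesic effect. Neutral wording is one of the few protections such a design has.

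Here the two techniques are introduced on different terms. One comes with published benefit and regulatory status, the other with a one-word description of what it does. The person giving the account also performs the procedure. F.2 summarises the content and gives no fixed wording, although several co-investigators will deliver it, so the emphasis may also differ between them.

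The between-arm difference in pain is the trial's primary result and may inform a later non-inferiority trial. A shift created by the explanation would be read as part of that difference.

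**Working it through.** The point is textual, so the passages are set side by side first. The plan has no figure of its own to reproduce here. Its 30 completers rest on a cited rule of thumb, and the documents give no effect size, SD or margin from which to recompute them.

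| What the patient is told (F.2) | Device | Lidocaine |
|---|---|---|
| Regulatory status | Stated | Not stated |
| Published benefit | Stated, in children | None cited |
| Label implying an effect | None beyond the literature sentence | *Numbing* |
| Caveat | Little used in adults | None |
| Used at this hospital | Described as used at other institutions, on children | Yes, by some providers |
| Adult evidence from B.1 | Not mentioned (one positive study, one null trial) | Not mentioned (meta-analysis) |

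Two things follow. The description is uneven, since cited evidence and regulatory status appear on one side only. But the cues do not all point the same way: three of the rows (label, caveat, local use) could lead an adult to expect more from the injection.

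Existing safeguards: analyst blinding acts after the rating has been given, and the envelope limits the wish to please the operator. Neither removes an expectation formed beforehand.

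**Illustration for this pilot.** From the documents: 30 completers at 1:1, so 15 per arm; t-test; significance at P < 0.05 (sidedness not stated, taken as two-sided). Assumed: no true difference and a uniform expectation shift of b SD.

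- Degrees of freedom 28, critical value 2.048.
- Noncentrality = b × √(15/2) = 2.739b.
- b = 0: rejection rate 5.0%.
- b = 0.10 (noncentrality 0.274): 5.8%.
- b = 0.25 (0.685): 10.1%.
- b = 0.50 (1.369): 26.2%.

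The rates are the same whichever arm the shift favours. The pilot could not reveal a shift of this order: the 95% half-width for the difference is 2.048 × √(2/15) = 0.75 SD.

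**Illustration for a possible later trial.** From the documents: 90% power and two-sided 5%. Assumed: a margin of 0.5 SD, a shift of 0.1 SD, and the same wording carried forward. With the sample size set by the power condition, SE = 0.5/(1.960 + 1.282) = 0.154 SD.

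- Shift towards the device, true difference at the margin: false non-inferiority = P(Z > 1.960 − 0.1/0.154) = 9.5%, against 2.5% without a shift.
- Shift away from the device, true difference at the margin: P(Z > 1.960 + 0.1/0.154) = 0.5%.
- Shift away from the device, true difference zero: power = P(Z > 1.960 − 0.4/0.154) = 74%, against 90%.

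The consequence reverses with the sign, and the sign is what the documents do not give.

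**The case against.** A reader might infer that the explanation favours the device, and so would make a later false non-inferiority finding more likely. The documents do not support that step. Calling lidocaine numbing tells the patient that it works. The literature claim for the device is confined to children and is qualified in the same sentence. An adult offered a bee-shaped ice pack used on children might well expect more from the injection.

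A reader might also infer that unfavourable device evidence was left out selectively. It was not: the positive adult volunteer study is omitted along with the null trial. Item 2 also notes that the null trial's authors thought the timing of application might explain their result.

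Three further objections carry weight. The consent form and a question period come between this explanation and randomisation, and the form's text was not available; it may already be balanced. The non-inferiority trial is only a possibility, with no margin or wording in these documents. And a uniform shift leaves the within-arm SD unchanged, so a planning SD taken from the pilot would be unaffected.

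These limit the point without removing it. A balanced form would not justify an uneven spoken account given before it, and an unknown direction is itself a reason for neutral wording. The pilot's own estimate of the pain difference remains exposed.

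**Conclusion.** The point holds in a limited form. F.2 describes the two techniques on unequal terms shortly before an unblinded, self-reported primary endpoint, and neither analyst blinding nor the envelope deals with expectation. This is a plausible risk of bias, not a demonstrated one. Neither its direction nor its size can be determined from the documents.

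The figures above rest on assumed shifts; those for a later trial also rest on an assumed margin and sign. They show what a shift of a given size would do, not what this wording will do. Nor do they show how much rewording would gain, since the trial stays open-label either way. The conclusion covers F.2 only. It merits a cheap correction and does not call the design into question.

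**What to change.** In F.2, replace the present explanation with one short standardised text, given identically by all co-investigators. It should say that both techniques are used to reduce discomfort during catheter placement and that it is not known how they compare in adults. Take out the paediatric literature sentence and the FDA sentence as selling points, and do not leave *numbing* as the only label for lidocaine. If regulatory status has to be given, give it in the same neutral terms for both.

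Removing efficacy statements for both techniques is safer than reciting the evidence for both. An account that reports mixed adult results for the device and supporting adult data for lidocaine could simply tilt expectation the other way.

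Check the consent form against the new text and align it where they differ. An optional addition is one question on expected pain, answered before randomisation, so that expectation can at least be described.

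The cost is a wording amendment with IRB approval and a briefing of the co-investigators, plus one questionnaire item if the option is taken. No extra patients or staff are needed, and neither technique changes.
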